#### **6.7.4. Vital Signs**

The analyses described below will be conducted for the following vital signs assessments respectively:

- SBP (mmHg)
- DBP (mmHg)
- Heart Rate (bpm)
- Respiratory Rate (breaths/min)
- Body Temperature (°C)

In accordance with the baseline value definition in Section 5.1.2, the change from baseline will be derived as follows:

$$\text{Change (unit)} = (\text{post-baseline value} - \text{baseline value})$$

The following will be summarized for the Safety Analysis Set:

- Observed values and change from baseline at each assessed timepoint for each standard vital sign parameter using default summary statistics for continuous variables.

A listing of all vital signs data including derived change from baseline will be provided for the Safety Analysis Set.

#### **6.7.5. Electrocardiograms**

The following electrocardiogram (ECG) assessments will be taken at baseline:

- An overall assessment classified as normal or abnormal
- Abnormal assessments will be further classified as clinically significant or not clinically significant

At baseline assessment, the subject will be classified as abnormal if any (one or more) of the replicate assessments are classified as abnormal. Similarly, the abnormal assessment will be classified as clinically significant if any (one or more) abnormal assessments are classified as clinically significant. The subject will be classified based on the worst finding of triplicate 12-Lead ECG. A list of ECG assessments will be presented.

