^a Visit/dosing windows of ±3 days on either side of the scheduled visits/dosing are permitted. In case of a delayed or missed dose, the investigator should return subjects on the original visit/dosing schedule in relation to Day 1 for subsequent doses. The window of ±3 days is relative to Day 1 and applicable for all subsequent visits/dosing. The minimum of time between doses should be no less than 4 days and no more than 10 days. Subjects do not need to return to the clinical site for dosing on weeks without study visits noted above if subject/caregiver completes study drug administration at home. See footnote “r” below.

^b Visit window of ±5 days. For subjects who prematurely discontinue study drug, the End of Treatment (EOT) visit should be completed within 14 days of withdrawal and follow-up visits should be completed at 8 weeks (Safety FU) and 14 weeks (PK & ADA FU) after the last dose of study drug, where possible. Subjects should continue to complete study assessments as outlined above where possible, with the exception of study drug administration. Anti-drug antibody sample and PK sample collection will not need to be completed if study drug is prematurely discontinued other than at the PK & ADA FU visit.

^c

All subjects who do not achieve cDAPSA low disease activity (cDAPSA ≤ 14) for 2 consecutive visits starting at Week 24 (e.g. at Week 20 and Week 24) will be required to discontinue study drug as described in Section 7.1. Participation in the study should be continued, with EOT visit and assessments as described in Section 4.1 and in footnote b and n.

^d Vital signs include measurements of temperature, respiratory rate, systolic and diastolic blood pressure, and pulse. Measurements should be taken in a sitting position after 5 minutes' rest.

^e Electrocardiograms in triplicate will be recorded (one minute apart) after subject has been supine for at least 5 minutes.

^f Chest x-ray (posterior/anterior or anterior/posterior) will be performed at screening in subjects who do not have a chest x-ray available within 3 months of screening. Women of childbearing potential must have a negative pregnancy test before an x-ray is performed.

^g Serious adverse events should be recorded from the signing of informed consent through the Safety Follow-up visit (ie, 8 weeks after the last dose of study drug); adverse events will be recorded from Day 1 (ie, administration of study drug) until 4 weeks after the last dose of study drug.

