8.2.5. Electrocardiograms

TriPLICATE 12-lead ECGs will be obtained one minute apart after subject has been supine for at least 5 minutes as outlined in the SoA ([Section 1.3](#)) using an ECG machine that automatically calculates the heart rate and measures PR, QRS, QT, intervals.

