9.3.5. Safety Analyses

Safety data will include summaries of exposure, AEs, TEAEs, SAEs, and laboratory data. No inferential statistics (*p*-values) will be reported for safety data.

Exposure will include the number of doses administered (including complete and incomplete doses) and reasons for missed or incomplete doses. Exposure will be reported through the planned collection of the primary endpoint and for the entire study. For subjects assigned to receive placebo who later receive izokibep, exposure will further be summarized by placebo and izokibep. Compliance will be summarized by placebo and izokibep and by phase (placebo controlled and after crossing over to active).

Adverse events and SAEs reported before the first administration of the study drug will be listed. All summaries will include only treatment-emergent events. The number of subjects who report 1 or more AEs, the number who report 1 or more severe AEs, the number who report 1 or more SAEs, and the number who report 1 or more AEs that lead to discontinuation of study drug will be summarized by treatment group during the primary phase of the study and overall. Subjects assigned to receive placebo who later receive izokibep will additionally be summarized by phase (placebo-controlled and after crossing over to active).

Laboratory data including ADAs will be summarized by treatment group and overall, at each planned collection timepoint.

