#### **2.7.5. Electrocardiograms**

Tripple 12-lead ECGs will be obtained to calculate the heart rate and measure PR, QRS and QT intervals.

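### SAP 6.7.5 describes ECGs at baseline only and gives only a listing, so ECG findings short of an adverse event get no by-arm summary at Week 16 or later

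*SAP*

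**What the plan says.** **Collection.** Protocol 1.3 marks the 12-lead ECG row at four visits and adds in a footnote: "Electrocardiograms in triplicate will be recorded (one minute apart) after subject has been supine for at least 5 minutes". Protocol 8.2.5 has the tracings made "using an ECG machine that automatically calculates the heart rate and measures PR, QRS, QT, intervals". SAP 2.7.5 carries this over as a safety variable: "12-lead ECGs will be obtained to calculate the heart rate and measure PR, QRS and QT intervals".

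**Analysis.** SAP 6.7.5 begins "The following electrocardiogram (ECG) assessments will be taken at baseline" and names two assessments: normal or abnormal overall and, if abnormal, clinically significant or not. The rule for combining replicates reads "At baseline assessment, the subject will be classified as abnormal if any (one or more) of the replicate assessments are classified as abnormal", with a parallel rule for clinical significance. The only output is "A list of ECG assessments will be presented". PR, QRS and QT are not mentioned again in the SAP's methods section.

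**Neighbouring sections.** For vital signs, SAP 6.7.4 plans "Observed values and change from baseline at each assessed timepoint for each standard vital sign parameter using default summary statistics for continuous variables". SAP 6.7.3 plans change from baseline, reference-range shifts and toxicity-grade shifts for laboratory data. SAP 6.7.6 states explicitly that physical examination findings will only be listed.

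**The concern.** The SAP's account of when ECGs are taken does not match the protocol's schedule, and the mismatch carries into the analysis. Followed as written, the plan gives post-baseline ECGs no subject-level classification, no shift from baseline and no interval summary by arm.

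At stake is the one placebo-controlled look at on-treatment ECGs. The placebo group starts izokibep at Week 16, so the End of Treatment and Safety Follow-up ECGs cannot replace it. There is also some reason to want the comparison. Major cardiovascular events are an event of special interest (Protocol 8.3.6), and Protocol 2.2.1 lists conduction disturbances among the cardiovascular manifestations of psoriatic arthritis. Against that background, individual abnormal tracings are hard to interpret without the placebo arm beside them.

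**Working it through.** No sample size, power or alpha figure is involved. The check sets the texts side by side.

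1. **Visit weeks.** The schedule's columns run Screening, Day 1, Weeks 1, 2, 3, 4, 8, 12, 16, 17, 18, 20, 24, 32, 36, 40, End of Treatment, Safety Follow-up, PK/ADA Follow-up. By position, the ECG marks fall in Screening, Week 16, End of Treatment and Safety Follow-up. As a test of the alignment, the anxiety and depression scale is due at baseline, Week 16 and Week 52 under its exploratory endpoint, and its marks fall in Day 1, Week 16 and End of Treatment. The alignment holds.

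2. **Which ECG is baseline.** There is no Day 1 ECG mark. SAP 5.1.2 takes the last non-missing value before randomization, so the screening ECG is the baseline value.

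3. **Which post-baseline ECG has a placebo comparison.** Protocol Section 8 puts assessments before dosing. SAP 5.1.3 ends Period 1 after the Week 16 assessments and before that visit's dose. Protocol 4.1 moves the placebo group to izokibep from Week 16. So the Week 16 ECG lies inside the placebo-controlled period, and the two later ones do not.

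4. **Planned ECG output against schedule.**

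| Scheduled ECG | Triplicate rule stated in SAP 6.7.5 | Summary table by arm |
|---|---|---|
| Screening (baseline) | Yes | None |
| Week 16 | No | None |
| End of Treatment | No | None |
| Safety Follow-up | No | None |

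The baseline row also has no table, because ECG is absent from the baseline characteristics in SAP 6.4.2. The triplicate rule therefore feeds no table anywhere.

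5. **Size of the listing.** If it covers every scheduled ECG, it holds up to about 325 subjects × 3 replicates × 4 visits = 3,900 tracings, of which 325 × 3 = 975 are from Week 16. A reader cannot compare arms from that without tabulating it.

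6. **What reaches a by-arm table another way.** Protocol 10.3.1 counts ECG results, including those that worsen from baseline, as adverse events when the investigator judges them clinically significant. SAP 6.7 and 6.7.2 tabulate treatment-emergent events by arm in Period 1. What remains without a by-arm summary is:
   - abnormal tracings judged not clinically significant
   - changes in PR, QRS and QT

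**The case against.** The strongest reply is that the clinically important part is already covered. Clinically significant ECG changes become adverse events, are tabulated by arm, and have major cardiovascular events tabulated among the events of special interest. This stands, and it narrows the point. A reader might infer that izokibep and placebo cannot be compared on ECG safety at all, and the documents do not support that. The adverse event route does depend on investigator judgment. It also leaves out findings attributed to the underlying disease unless they are more severe than expected (Protocol 10.3.1).

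Second, the SAP breaks no promise in the protocol. Protocol 9.3.5 says "Safety data will include summaries of exposure, AEs, TEAEs, SAEs, and laboratory data", and the secondary safety endpoints in Protocol Section 3 do not include ECG. This also stands: the gap is in safety reporting, not a departure from a named endpoint. Yet Protocol 9.3.5 does not name vital signs either, and the SAP summarizes those.

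Third, listing alone is an accepted treatment, as for physical examination. But SAP 6.7.6 says so openly and covers each assessment, whereas SAP 6.7.5 has no such statement and misdescribes when ECGs are taken. That looks more like an omission than a decision. The ECG listing is not restricted to baseline, so later tracings may well appear in it.

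Fourth, a reader might argue from an untested dosing frequency. Protocol 4.3 reports no dose-limiting safety or tolerability up to 160 mg weekly across indications, and neither Protocol 2.3.1 nor 8.3.6 names a QT, rhythm or conduction risk for izokibep. The point should not lean on dose novelty.

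Finally, the eCRF is not available here. The machine measures the intervals, but SAP 6.7.5 names only classifications, so capture of interval values in the database is unconfirmed.

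**Conclusion.** The point holds as a limited safety-reporting gap. Three scheduled post-baseline ECG visits have no planned by-arm summary. One of them, Week 16, is the only scheduled on-treatment ECG with a randomized placebo comparison. The loss is confined to abnormal findings judged not clinically significant and to interval changes.

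Two stronger readings should be resisted. The plan does not summarize baseline ECGs while neglecting the others, since baseline gets only a rule and a listing. Nor can the size of any missed difference be stated, because the documents give no ECG abnormality rate for either arm.

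The conclusion assumes that the visit weeks are read correctly from a table with imperfect layout, and that no separate table shell adds the missing output. No efficacy endpoint, hypothesis test or error rate is touched.

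**What to change.** In SAP 6.7.5:

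- Replace the baseline-only wording with the protocol's ECG visits, and apply the worst-of-triplicate rule at each.
- Add a shift table from baseline to Week 16 by arm on the Safety Analysis Set, with three categories: normal, abnormal not clinically significant, abnormal clinically significant.
- Add a Period 2 shift table to End of Treatment, using the SAP 6.7 groupings.
- State where an End of Treatment ECG from a subject who stops drug before Week 16 is counted, since the visit mapping in SAP 5.1.4 covers efficacy assessments only.
- If interval values are in the database, summarize change from baseline in the triplicate means of PR, QRS and a heart-rate-corrected QT, with the correction named in advance. Uncorrected QT alone would mix rate changes with interval changes. If the values are not captured, say so and reconcile this with SAP 2.7.5.

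The change should be made before unblinding. It costs a few safety tables, with no new visits and no alpha. The shift tables rest on the classifications SAP 6.7.5 already names. The interval summary depends on data capture.

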### **6.7.6. Physical Examination**

Clinically significant findings observed prior to the first dose of study drug will be entered in the CRF and reported as medical history. Clinically significant findings observed after the first dose of study drug will be reported as AEs in the CRF and reported as AEs.

Physical examination findings (normal/abnormal/clinically significant) and details of abnormalities will be listed only for each subject at each assessment.

### **6.7.7. Interim Analysis and Data Monitoring**

An independent Data Monitoring Committee (DMC) will be established to monitor data on an ongoing basis to ensure the continuing safety of the subjects enrolled in this study.

The DMC will consist of two clinicians and a biostatistician that, collectively, has experience in the management of subjects with Psoriatic Arthritis and in the conduct and monitoring of randomized clinical trials. The DMC responsibilities, authorities, and procedures will be documented in the DMC charter. The committee will meet approximately every 6 months to review interim data. After each review, the DMC will make recommendations regarding the continuation of the study based on safety.

The DMC will review unblinded efficacy data when approximately 120 subjects have had the opportunity to complete the Week 12 visit. Data from the first 105 subjects randomly assigned to receive izokibep 160 mg QW, izokibep 160 mg Q2W or placebo will be used for these DMC summaries. The DMC may make a recommendation on further development activities for izokibep based on this data review. The DMC will not be empowered to recommend stopping this study or changing the sample size due to a demonstration of positive efficacy. The study team operationalizing the day-to-day of the study, the subjects, and the investigators will remain blinded to these interim results until after the study is completed.

No interim analyses will be conducted for the purpose of stopping the study or altering the study design.

The primary analysis of primary and secondary endpoints will occur after all subjects have had an opportunity to complete the Week 16 assessments (have completed the Week 16 assessments, or have completed a subsequent timepoint assessment, or permanently discontinued the study before Week 16). For the primary and secondary objectives, this will include all data for all subjects for the final analysis, and so it will be the final analysis. The final analysis will be conducted at the end of the study when all subjects have completed the study or permanently discontinued the study. For the primary endpoint, all available data at visits after Week 16 will be included in the summaries at these timepoints, but some

subjects will be ongoing and may have data collected after the primary analysis is reported. Data collected at subsequent timepoints may be summarized when all data at that timepoint have been collected. All data collected for the primary endpoint for all subjects through the end of the study will be reported in a subsequent analysis, but the p-values from each comparison of a regimen of izokibep to placebo in this subsequent analysis will not be used for any alpha-preserving hypothesis testing. Investigators, site personnel, and all sponsor personnel who have contact with subjects will remain blinded to individual subject treatment assignments until the final analysis.

When the primary efficacy analysis is conducted, safety data will be summarized. Summaries will include all safety data through Week 16 and all available safety data on all subjects through the end of the study. All safety data will be summarized through the end of the study when all subjects have completed all visits.

## 6.8. Pharmacokinetic Assessments

PK concentrations will be summarized by dose group and scheduled visit. Summary statistics will be reported with the number of samples, number of samples that are BLQ, arithmetic mean, standard deviation, coefficient of variation in percent (CV), minimum, median, maximum, geometric mean and the CV of the geometric mean in percent. For the calculation of summary statistics, predose concentrations that are below the limit of quantification (BLQ) will be treated as zero and post-dose concentrations that are BLQ will be treated as missing.

Plots of arithmetic mean time courses by dose group will be provided using linear and semi-logarithmic scale.

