^h Joint assessment will be performed for ACR66/68 and DAS28 joints for swollen and tender joint counts.

ⁱ Radiographs of hands/wrists/feet will be done on all subjects who discontinue from the study drug or the study at Week 16 or later and it has been at least 12 weeks from the time the last radiographs were obtained. Radiographs should be obtained as close as possible to the EOT date.

^j Hepatitis B surface antigen will be conducted. A positive result for the HBsAg will be exclusionary. Samples negative for HBsAg will be tested for HBsAb and HBcAb. If test results are positive for HBcAb or HBsAb, then HBV DNA polymerase chain reaction will be performed and any result that meets or exceeds detection sensitivity will be exclusionary.

^k QuantiFERON test (or equivalent) for TB will be performed. Note: T-SPOT testing may be allowed after consultation with medical monitor.

^l Serum pregnancy test required for screening and urine pregnancy test required at all other times for WOCBP. Local authorities may require more frequent pregnancy testing.

^m Fecal calprotectin at screening only required if subject has: a) Prolonged or recurrent diarrhea b) Prolonged or recurrent abdominal pain c) blood in stool or d) any other symptoms in the opinion of the Investigator that may be suggestive of IBD

ⁿ Pharmacokinetic and anti-drug antibody blood sampling will be taken prior to administration of study drug (predose) on dosing days. For subjects who prematurely discontinue study treatment for any reason, follow-up sampling should be taken at a PK & ADA FU visit 14 weeks after the last dose of study drug where possible, but do not need to be completed at other timepoints.

^o Subjects will be monitored at the study site for at least 1 hour after study drug administrations for the following visits: Day 1/Week 0, Week 1, Week 2, Week 16, Week 17, and Week 18.

^p After Week 4, subjects may perform home dosing of study drug at weeks without study visits (see footnote "a") and do not need to return to the clinical site on those weeks. Subjects may begin self-administration of study drug from Week 5. Subjects will be trained on study drug handling and self-administration of study drug at the study visits prior to beginning self-administration. Subject's caregiver or designee can also be trained on home dosing based on subject's preference.

^q Last dose of study drug will be administered on Week 51.

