End of Study Visit will be conducted at Week 65. For subjects that prematurely discontinue study drug for any reason, the EOT visit should be completed within 14 days of withdrawal, Safety follow-up visit should be completed at 8 weeks and PK/ADA follow-up visit should be completed 14 weeks after the last dose of study drug, respectively, where possible. Subjects should continue to complete study assessments as outlined in the SoA (Section 1.3 of 22104 protocol) where possible, with the exception of study drug administration and anti-drug antibody sample and PK sample collection.

The final analysis of primary and secondary endpoints will be conducted after the last subject has had the opportunity to complete Week 16 assessments or prematurely discontinues the study drug and/or study.

Before database lock, an error was discovered in dosing for subjects who were randomized to receive izokibep 160 mg every 2 weeks (Q2W) from Day 1/Week 0 to Week 50, with matching placebo Q2W and subjects who were randomized to receive izokibep 80 mg every 4 weeks (Q4W) from Day 1/Week 0 to Week 48, with matching placebo QW until Week 51. Subjects were assigned study drug in groups of four visits at a time. The order in which the subject was instructed to receive the drug was incorrect. Therefore, each subject was assigned the correct amount of study drug over each 4-week period, but possibly in the wrong sequence, resulting in subjects who were randomized to receive active drug Q2W receiving active drug on two or more consecutive weeks and/or placebo at two or more consecutive weeks. Subjects who were randomized to receive active drug Q4W similarly received active drug at two or more consecutive weeks and/or placebo at four or more consecutive weeks. As a result of this error, the following changes were made to the analysis plan:

- Testing of all primary and secondary endpoints, comparing izokibep Q2W versus placebo, will only be done after testing of all primary and secondary endpoints, comparing izokibep QW versus placebo, in the alpha-controlled testing sequence.

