  - Justification: subjects randomized to receive izokibep Q2W received the correct amount of study drug, but in incorrect order. Some quantities will be as planned (total drug received, possibly area under the concentration-time curve) while others may not ( $C_{trough}$ ,  $C_{max}$ , possibly area under the concentration-time curve). Therefore the group that was treated as planned will be tested first, and the group treated not as planned will be tested second.
- Exploratory analyses of the impact of incorrect dosing will be evaluated during Period 1.
  - Subjects randomized to receive izokibep Q2W will be grouped according to the largest number of consecutive doses of active drug received to understand the impact of various dosing schedules on outcome.

- Summaries of subjects dosed correctly at earlier time points (week 4 and 12 for the primary endpoint).

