- Change from baseline in LEI at Week 16, 24, 52
- Time to resolution of enthesitis at weeks 4, 12 and 16 among subjects with enthesitis (LEI > 0) at baseline
- Occurrence of enthesitis (LEI > 0) at week 4, 12 and 16 among subjects without enthesitis (LEI = 0) at baseline
- HADS change from baseline to Weeks 16 and 52
- Decrease of at least 2 from baseline in LEI, among subjects with baseline LEI of at least 2, at weeks 4, 12 and 16
- Subject's Global Impression of Change Questionnaire at weeks 16 and 52
- AUC for ACR-N through week 16
- Time to first achievement of ACR50
- Time to first achievement of PASI90 among subjects with at least 3% BSA at baseline
- Time to first achievement of MDA
- Time to first achievement of ACR20
- Time to first achievement of PsAID improvement of at least 3 among subjects with PsAID at least 3 at baseline
- Time to first achievement of PASI100 among subjects with at least 3% BSA at baseline
- Trough plasma concentrations of izokibep at collected timepoints
- Presence of anti-drug antibodies (positive or negative)

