#### 5.1.4. Visit Windows

All data will be analyzed using the nominal study visit as defined in the SoA in the protocol and eCRF.

In the event that a subject discontinues the study early, the subject will have an early termination visit which includes efficacy assessments. If the early termination visit or an unscheduled visit occurs in a timeframe that corresponds to a scheduled efficacy assessment (week 2, 4, 12, 16, 20, 24, 32, 36, 40 or 52), and if the subject does not have an actual visit at or after the corresponding scheduled efficacy assessment, the following day ranges will be used to map the early termination/unscheduled visit to a scheduled efficacy assessment for use in all efficacy summaries at that timepoint. Similarly, if an unscheduled efficacy assessment occurs during a timeframe that corresponds to a scheduled efficacy assessment, it will be windowed accordingly, provided the subject does not have an actual visit at the same nominal time.

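### After the dose-sequence error, the PK tables by scheduled visit can mix different intervals since the last active dose in the Q2W and Q4W arms, and no PK summary was added to show this

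*SAP*

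**What the plan says.** SAP 2.6 lists the PK endpoint as "Trough plasma concentrations of izokibep at collected timepoints". The footnotes to the protocol's Schedule of Activities (1.3) fix the sampling time: "Pharmacokinetic and anti-drug antibody blood sampling will be taken prior to administration of study drug (predose) on dosing days". Every arm is injected weekly, so in Q2W and Q4W the injection that follows a sample may be placebo.

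SAP 6.8 sets the summary rule, "PK concentrations will be summarized by dose group and scheduled visit", and adds plots of arithmetic means over time by dose group. SAP 6.6.5 repeats the rule. Under SAP 5.1.4, "All data will be analyzed using the nominal study visit as defined in the SoA in the protocol and eCRF".

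SAP 2.1 describes the dosing error: "each subject was assigned the correct amount of study drug over each 4-week period, but possibly in the wrong sequence". The consequence for Q2W was "receiving active drug on two or more consecutive weeks and/or placebo at two or more consecutive weeks"; Q4W subjects "similarly received active drug at two or more consecutive weeks and/or placebo at four or more consecutive weeks". In justifying the new test order, the SAP says of the Q2W arm that "Some quantities will be as planned (total drug received, possibly area under the concentration-time curve) while others may not" be, and names the trough concentration among the latter.

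The analyses added because of the error concern testing order and efficacy: ACR50 by longest run of consecutive doses and ACR50 at Week 12 in correctly dosed Q2W subjects (6.6.2), and early endpoints at Week 4 (6.6.5). Section 6.6.5 states that sequencing was correct for all subjects at Week 4. Section 6.6.2 expects few Q2W subjects to have had no consecutive doses. No PK table is split by sequence or by time since the last active dose.

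**The concern.** A trough at a given visit is interpretable when the samples in the cell share the same interval since the last active dose. In Q2W and Q4W after Week 4 they need not. A cell mean would then average over several intervals, and its SD and CV would show sequence error as if it were between-subject variability. SAP 6.6.2 compares ACR50 across Q2W subsets that it describes as differing in PK, but no planned table shows PK for those subsets. What is at stake is whether the descriptive PK results for these two arms can be read as steady-state troughs of the planned regimens.

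**Working it through.** **Inputs**
- Half-life after single SC doses: 278 h, individual range 199 to 464 h. After repeated dosing: 279 h, range 229 to 423 h. Median t_max after a single SC dose: 60 h (protocol 2.2.3.4).
- Predicted steady state for 160 mg QW: AUC 5850 h·µg/mL, C_average 34.8, C_max 40.8, C_min 27.2 µg/mL (protocol 4.3, Table 2).
- Drug assigned four visits at a time, correct amount per block (SAP 2.1); correct sequence up to Week 4 (SAP 6.6.5).

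**Assumptions, not in the documents:** blocks start at Weeks 0, 4, 8 and 12; any order within a block is possible; PK is linear.

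**Interval since last active dose at the Week 16 predose sample**
- Q2W, planned: last active dose at Week 14, so 2 weeks. With two active doses anywhere in Weeks 12 to 15, the last falls at Week 13, 14 or 15, so 3, 2 or 1 weeks.
- Q4W, planned: last active dose at Week 12, so 4 weeks. With one active dose anywhere in Weeks 12 to 15: 4, 3, 2 or 1 weeks.

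**Decay between the extremes**, ratio = 2^(difference in hours / half-life)
- One week: 2^(168/278) = 1.52.
- Q2W, 1 against 3 weeks: 2^(336/278) = 2.31. Over half-lives of 464 to 199 h: 1.65 to 3.2.
- Q4W, 1 against 4 weeks: 2^(504/278) = 3.5. Over the same range: 2.1 to 5.8.

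**Check with accumulation from earlier doses**

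The plan's own figure first: C_average = AUC/τ = 5850/168 = 34.8 µg/mL, which reproduces Table 2.

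A one-compartment model with first-order absorption then uses CL/F = 160,000/5850 = 27.4 mL/h and ke = ln 2/279 = 0.00248 per hour. Solving ln(ka/ke)/(ka − ke) = 60 gives ka = 0.0537 per hour. For QW at steady state the model gives C_max 38.7 and C_min 29.4, against 40.8 and 27.2 stated (within about 8%), which is adequate for ratios.

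With Weeks 0 to 3 correct and the next three blocks free, there are 6³ = 216 Q2W and 4³ = 64 Q4W sequences. Week 16 predose concentrations (µg/mL):

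| Arm | As planned | 1 week | 2 weeks | 3 weeks | 4 weeks |
|---|---|---|---|---|---|
| Q2W | 11.7 | 14.6–20.4 | 11.2–14.8 | 8.9–11.0 | – |
| Q4W | 1.8 | 5.4–6.2 | 3.6–4.4 | 2.5–3.3 | 1.8–2.6 |

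The full spread is 20.4/8.9 = 2.3-fold for Q2W and, from unrounded values, 6.15/1.77 = 3.5-fold for Q4W, in line with the simple decay figures. Relative to the planned trough, Q2W runs from 0.76 to 1.75 times and Q4W from 1.0 to 3.5 times. For half-lives of 229 to 423 h, a sample one week after active drug is 1.1 to 1.95 times planned for Q2W and 1.9 to 4.6 times for Q4W.

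**The case against.** A reader might infer more than the documents support, and several points against a stronger reading stand.

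- **Dose-response.** One might conclude that the dose-response reading rests on mixed sampling times. It does not: protocol 9.3.4 and SAP 6.6.5 assess dose-response qualitatively from the primary and secondary endpoints. No formal comparison of exposure between arms is planned.
- **What the SAP concedes.** One might read SAP 2.1 as accepting that troughs are off plan in both arms. It says they may be, and the sentence concerns Q2W. For Q4W the same possibility follows from the description of the error, not from that sentence.
- **Not a trough at all.** This goes too far. Visits through Week 4 and the QW arm are unaffected by this error, and some later samples will fall at the planned interval. As far as the schedule can be read, early weekly samples in Q2W and Q4W fall at varying intervals even under correct dosing, so the endpoint already means predose at collected times.
- **Fold-changes.** They compare extremes. If all orders were equally likely (an assumption), 1 in 6 Q2W subjects would be at 3 weeks.
- **Partly covered.** The error is disclosed, minimum and maximum are reported so wide dispersion would show, administration data are listed, and protocol 9.3.4 allows pooled PK modeling that could use actual times.

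These points limit the consequence but do not close the gap. Dispersion in a visit cell does not show its cause, and optional modeling does not label or correct the planned tables.

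**Conclusion.** The concern holds in a limited form. As written, the SAP would present Q2W and Q4W predose concentrations after Week 4 under a trough label although the interval since active drug can differ between subjects in the same cell. Under aligned blocks and free order, the possible Week 16 spread is about 2.3-fold for Q2W and 3.5-fold for Q4W. Under the same assumptions the Q4W shift can only be upward at visits that close a block, because the planned first position already gives the longest interval. If blocks do not line up with sampling visits, intervals could be longer. The documents do not give the sequences received, so the average shift cannot be estimated.

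The consequence is confined to the exploratory PK endpoint and its descriptive tables and plots. No alpha-controlled test and no planned dose-response analysis depends on it. This is an inexpensive improvement, not a threat to the trial's conclusions.

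**What to change.** Keep the visit table in SAP 6.8 with all samples. Add a footnote that Q2W and Q4W values after Week 4 are predose concentrations affected by the sequence error and not necessarily troughs at the planned interval; mark the mean plots likewise.

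Add one table for Q2W and Q4W giving concentrations by visit and actual whole weeks since the last izokibep dose, and optionally by the consecutive-dose subsets of 6.6.2. The data exist: protocol 8.4 records the date and time of each sample, protocol 6.4 records dose dates, and SAP 6.6.2 already classifies subjects by doses actually received.

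Do not restrict the visit table to samples at the planned interval. Earlier doses may still be out of order, so those samples need not recover the planned trough: in the model they range over 11.2–14.8 against 11.7 µg/mL for Q2W and 1.8–2.6 against 1.8 for Q4W. The restriction would also discard exposure the subjects actually had.

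The cost is one extra descriptive table with small cells, especially in Q4W: 25 subjects over four intervals is about 6 per cell if orders were equally likely.
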